Analysis Plan. We will begin qualitative analyses shortly after data collection commences. The study team will meet regularly to review all data, and listen to and discuss key segments of the recorded interviews. Analyzing qualitative data as it is collected is crucial to monitoring data quality, refining observation and interview guides, and monitoring theme saturation. This ongoing process will be used to track emerging themes and create a coding template to be used for more in-depth analysis. We will follow the 5-phase analysis strategy described by Miller and Crabtree (describing, organizing, connecting, corroborating/ legitimizing, representing).^{34,35} We will use an immersion-crystallization approach in which the team reads and discusses the data for each clinic (immersion) to identify key findings (crystallization);^{35,36} we will do this twice, first to identify key themes within each “case” CHC, and then to identify cross-case finding.

The survey data and interview transcripts will be coded using the 5-phase analysis strategy explained above. We will also analyze differences between the Phase I and Phase II clinics’ experiences with APM implementation.

Quantitative data collection

We will compile EHR and Medicaid claims datasets that include data from up to 3 years pre-APM implementation, during implementation, and ≥ 3 years post.

Aims 1 and 2 Evaluation Summary				
Evaluate effect of APM intervention on:	Study Time Periods	Data Sources	Inclusion Criteria	Analyses
Aim 1. Internal services utilization and quality of care delivered; Aims 2 & 3. Utilization of and spending on services outside of the CHC,	Up to 3 years pre-APM implementation; ≥ 3 -years post-APM implementation;	1. Internal services: OCHIN EHR data 2. External services and expenditures:	1. Total clinic population: established patients at intervention and control clinics aged 2-64 2. Medicaid	Clinic level analysis using the DID analysis and patient level analysis using Generalized Estimating Equation models, to accommodate serial and intra-clinic correlations, categorical and continuous covariates, fixed and time-dependent covariates. Two-part models will be used to accommodate distributions

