Econometric analyses. Using difference-in-differences methods, we will calculate the average pre-post APM difference in spending of patients in APM intervention clinics, subtracted by the average difference among patients in comparison clinics. Changes in spending after APM implementation in the intervention

clinics vs. spending changes in the control clinics will “net out” any secular changes not related to APM. Any remaining significant differences in outcome – the DID – are attributed to the APM intervention. These findings will help to assess whether the APM intervention can help reduce costs, and if so, whether the reduction comes from lower spending at the CHC level or through reductions in potentially unnecessary or inefficient use of specialty and hospital services. We note that CHCs are not financially at risk for services outside of the CHC and thus do not have incentives to act as gatekeepers to care. Thus, reductions in spending for specialty services and other external services would most likely reflect improvements in internal care delivery.

Analytically, the difference-in-differences estimate is represented by the marginal effect on the interaction between a dummy variable indicating that the observations occur in the post-APM period and a dummy variable indicating the individual’s attribution to an APM intervention clinic. We will also include patient-level variables to account for predisposing factors and need for services. A variety of issues must be addressed in our DID estimation:

Definition of external services. External services will be defined as any care occurring outside of the CHC, e.g., emergency department visits, hospitalizations, and other ambulatory care that takes place in settings other than the CHC.

Accounting for clinic-level effects. Our study will focus on the “treatment-effect” of the APM: how does the transition to a capitated payment system affect health care spending? Since this is our main focus, our approach may include use of clinic-level fixed effects to net out any time-invariant differences in clinic-level cost outcomes. However, recognizing the potential interest in clinic-level effects, in secondary analyses we will test hierarchical (mixed) models to more specifically model (i) clinic-level variation and (ii) patient-level variation.

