Modeling health care costs. As in many analyses of a patient’s health care costs, in any given year, many patients will have no visits or expenditures. Thus, our dependent variable will have a cluster of observations at zero. We will use a well-validated approach for modeling this phenomenon: the 2-part model.⁵³ Part 1 will use a logistic regression to estimate the probability of any expenditure. Part 2 will focus on individuals with non-zero expenditures. We will use recent literature to guide the appropriate estimation approach, taking into account the potentially skewed distribution of the dependent variable.^{54,55}

Accounting for all expenditures. Estimates of changes in spending must account for all expenditures, including capitated and fee-for-service (FFS) payments. Of note, Oregon’s Medicaid managed care organizations (MCOs) provide encounter data to the state Medicaid agencies in lieu of FFS claims, a common practice in many states. These data are assessed for general accuracy and consistency and have been used by states to set managed care payment rates. In order to attach “paid” amounts to these encounter claims, we will impute a “paid” amount across all FFS and MCO claims (that is, any external services for which there would be payment outside of the APM capitation rate) based on the median FFS payment. The study team has used this approach previously and has extensive experience in the data structures, elements, values, means of combining records and methods for aggregating and measuring service dimensions.^{25,56} In summary, creation of the expenditure variable will be based on a blend of actual FFS payments, recorded capitation rates, and, where necessary, imputed expenditures that have served as the actuarial basis for rate setting in Oregon.

Modeling interaction terms. In non-linear models (e.g., the 2-part model) the interpretation of the interaction effect cannot be directly calculated from the coefficient on the interaction term.⁵⁷ Our approach will be to estimate the 2-part model, save those coefficients, and use empirical simulation (also known as “recycled predictions”) methods to determine the APM’s average effect using bootstrapping to derive 95% confidence intervals.

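### Must the plan name its Part 2 cost estimator for total Medicaid spending (Hypothesis 2b), given that the APM itself changes how clinics are paid?

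*Combined protocol and SAP*

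**What the plan says.** The Aims 1 and 2 Evaluation Summary table lists total Medicaid spending in a row whose analysis column says "Two-part models will be used to accommodate distributions" of spending. Modeling health care costs gives the reason, that "our dependent variable will have a cluster of observations at zero". It names logistic regression for Part 1. For Part 2 it gives the population, "Part 2 will focus on individuals with non-zero expenditures", and then "We will use recent literature to guide the appropriate estimation approach, taking into account the potentially skewed distribution of the dependent variable". The two references at that sentence concern, by title, retransformation of a logged outcome under heteroscedasticity and whether to log-transform at all.

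Accounting for all expenditures builds the outcome from "a blend of actual FFS payments, recorded capitation rates, and, where necessary, imputed expenditures" and applies imputed amounts to "any external services for which there would be payment outside of the APM capitation rate". Background and Significance explains that the APM turns visit-based revenue into a monthly payment per member. Modeling interaction terms obtains the effect by recycled predictions with bootstrap intervals.

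Econometric analyses starts from a plain difference of mean pre-post changes. It then adds covariates ("We will also include patient-level variables to account for predisposing factors and need for services") and asks "whether the reduction comes from lower spending at the CHC level" or from less specialty and hospital use.

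**The concern.** In most cost evaluations the intervention leaves the payment mechanism alone, so the choice among standard Part 2 models is a second-order matter. Here the intervention is a payment mechanism. On the natural reading, only APM patients in the post-period move from visit payment to a flat amount. That removes zeros in that cell and weakens the link between need and spending there. Both changes fall in the cell that identifies the interaction. Estimators that weight large and small spenders differently could then report different effects although neither care nor mean spending changed. Hypothesis 2b predicts a fall in total spending, so an artefact of several points in either direction would matter, and an unnamed estimator leaves room to choose after seeing results.

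**Working it through.** **Inputs.** The documents give no mean cost, monthly rate, zero share or variance, so there is no planned figure to reproduce. All of the following are assumptions: mean spending $4,000 a year; zero share 10, 25 or 40%; clinic share of spending 15, 30 or 50%; external spending in 60% or 100% of users (3 x 3 x 2 = 18 scenarios); 20,000 patients per cell; 60 replicates (30 for the slope and flat-rate checks); one standard normal need covariate (logit slope 0.8 for any use, log slope 0.5 for external cost); budget-neutral monthly payment in the APM post-period only; true effect zero.

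**Step 1: no covariates.** Let p be the Part 1 probability and m the Part 2 mean. The effect is p(on) x m(on) - p(off) x m(off), with the interaction switched on and off in APM-post. A saturated log-link GLM reproduces each cell's mean of positives, and Part 1 reproduces each cell's proportion, so p x m is the cell mean. If the other three cells are alike, the off prediction is their common mean, and the difference is 0 whatever happened to the zeros. With 100% positive spending in APM-post, p(on) tends to 1 and the effect stays finite.

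A separate cost model without covariates agrees: the GLM returns 0.0 throughout. Log-OLS with one smearing factor for all cells does not. It gives 365/2,805 = +13.0% at 3 visits a year and -1,206/2,294 = -52.6% at 0.5 visits. That method assumes the same error shape in all four cells, which is the hazard named in the title of the retransformation reference.

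**Step 2: with the need covariate.** Differences from a one-part log-link Poisson model on the same draws, in percentage points:

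| Condition | Poisson Part 2 | Gamma Part 2 | Log-OLS, separate smearing |
|---|---|---|---|
| Flat payment in APM-post only, full coverage | -0.02 to +0.08 | -8.1 to +3.5 | -6.7 to +2.8 |
| Same, no covariate | not listed | within 0.01 | -0.5 to +0.9 |
| Visit payment in all cells | within 1 | within 1 | within 1 |
| Flat payment in all cells | within 0.7 | within 0.7 | within 0.7 |
| Covariate slopes halved | not listed | -2.9 to +0.8 | not listed |
| Covariate slopes x 1.5 | not listed | -10.1 to +9.3 | not listed |
| 50% coverage | +0.1 to +1.7 | -3.9 to +2.0 | not listed |

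On $4,000, -8.1 points is -$324 and +3.5 points is +$140. One common smearing factor gives -25 to +9 points in the first row.

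**Step 3: where the extremes lie.** At the base slopes, gamma gaps below -5 points occur only with 40% zeros and a 15% clinic share, which is 2 of the 18 scenarios. At 10% zeros a repeat run gave -0.8 to +3.8. The two mechanisms oppose each other: flat payment with zeros kept moves gamma by +1.3 to +4.3, and removing the zeros adds -0.7 to -9.4.

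**Step 4: what a replacement would buy.** The obvious candidates are a one-part Poisson model, a linear difference-in-differences, or a Poisson Part 2. At 50% coverage the Poisson Part 2 drifts by up to 1.7 points, which favours the one-part model. If average need in APM-post shifts by 0.25 SD either way, the one-part model drifts by about +0.8 and -1.1 points while the two-part Poisson stays near 0, so the ranking reverses. Such shifts are plausible: Inclusion criteria says that clinic panels need not hold the same patients before and after. The one-part Poisson standard deviation is a median 1.18 times that of gamma and 1.5 times that of separately smeared log-OLS, so its variance is 1.18² = 1.39 and 1.5² = 2.25 times as large.

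**The case for a change.** The strongest reply is that a pointer to literature is not a rule. Statistical analyses also allows models to be refined in the light of preliminary analyses, and the sign of the artefact can change with the estimator. Bootstrap intervals reflect sampling error and do not cover the choice of model. A different cost model with a need covariate also showed divergence (gamma -0.8% to +5.6% in single runs), so the result does not hang on one simulation design. One added paragraph would cost little.

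Much of this stands. The estimator is unnamed, the mechanism is real, and the divergence disappears when payment form is the same everywhere, so skewness alone is not the cause. Naming the estimator and its retransformation, and saying which member-months carry the monthly payment, would be good practice.

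What does not stand is the step from an open detail to a flaw. No passage says which member-months carry capitation, and that attribution decides whether the problem exists. The widest range belongs to single-factor smearing, which the plan does not prescribe and which its cited topics warn against. The gap was never set against a realistic interval: without clustering, the one-part Poisson standard deviation was already about 0.5 to 4.5 points, and the trial has only 3 + 5 + 3 = 11 APM organisations.

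**Conclusion.** No change to the plan follows. The point is a gap that a competent cost analyst fills sensibly, and the proposed remedy is a trade-off. If the flat payment applies only in the APM post-period and need covariates are strong, ordinary Part 2 estimators can differ by a few points under a null. Larger gaps need extreme assumed inputs, such as 40% zeros with a 15% clinic share or slopes 1.5 times the base. The gap is negligible for a gamma Part 2 without covariates and within 0.7 points for every estimator if all cells are paid the flat rate.

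The plan already contains the main safeguards: a mean-based difference-in-differences as its starting definition, a split between clinic and external spending, and references on the retransformation problem. Hypothesis 2a, on external spending, is unaffected; under the same null the two-part models stayed between -0.8% and +0.8%. These sizes rest wholly on assumed inputs and concern point estimates only, since clustering was not simulated.
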